#### 9.13.1. Convulsions and Seizures

This AESI will be identified using Convulsion (SMQ) with narrow scope.

#### 9.13.2. Respiratory Adverse Events

This AESI will be identified using the System Organ Class and High Level Term as below.

SOC: “Respiratory, thoracic and mediastinal disorders”

HLT: “Respiratory and pulmonary function diagnostic procedures”

#### 9.13.3. Possible Distant Spread of Toxin

This AESI will be identified using the Preferred Term as below.

Accommodation disorder
Aspiration
Bradycardia
Botulism
Bulbar palsy
Constipation
Cranial nerve palsies multiple
Cranial nerve paralysis
Diaphragmatic paralysis
Diplopia
Dry mouth
Dysarthria
Dysphagia
Dysphonia
Dyspnoea
Extraocular muscle paresis
Eyelid function disorder
Eyelid ptosis
Facial paresis
Facial paralysis

CONFIDENTIAL

207660

Hyporeflexia
Hypotonia
Illeus paralytic
Muscular weakness
Paralysis
Paralysis flaccid
Paresis cranial nerve
Pelvic floor muscle weakness
Peripheral nerve palsy
Peripheral paralysis
Pneumonia aspiration
Pupillary reflex impaired
Respiratory arrest
Respiratory depression
Respiratory failure
Speech disorder
Urinary retention
VIIth nerve paralysis
Vision blurred
Vocal cord paralysis
Vocal cord paresis

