Section 10.13.	
 
Removed the two following PT to identify AESI since these were included in the list by mistake. 
 
Paralysis flaccid
 
Vllth nerve paralysis
 
 
 

CONFIDENTIAL

207660

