## CONFIDENTIAL

207660

Overview of Study Design and Key Features	
	
muscles that act on the finger (including thumb flexors) and wrist flexors, and 160 units into the muscles that act on the elbow flexors. A total of 400 units of the product will be injected.
 
 
• In the 240-unit group, 240 units of the product will be injected into the muscles that act on the finger (including thumb flexors) and wrist flexors. Placebo will be injected into the muscles that act on the elbow flexors. A total of 240 units of the product will be injected.
 
• In the Open-label phase, a total of 400 units will be injected in both groups. 
 
• The product can be injected up to 3 times after completion of Part 1 in the blind phase. Participants whom the investigator considers as eligible for the injections will be treated. The next injections cannot be performed until the eligibility of the participant has been confirmed by the investigator.
 
• The muscle to be injected and the dose will be decided by the investigator based on the patient's symptoms, and a total dose of 400 units of the product will be injected in a divided dose. For the muscles that the investigator considers as unnecessary to be treated, an injection may be skipped. The involving muscle and the dose do not have to be same each time always.
 
 
 

Treatment Assignment	
 
• Number of participants (randomized participants): 120 (60 per group)
 
• GSK RandAll NG will be used to generate the randomization schedule.
 
• The randomization will be stratified by the MAS score (3 or 4) in the elbow flexors at Day1
 

Interim Analysis	
 
• Interim analysis is planned in this study as described in 3.1.
 

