**10.4.2.1. Definition of Adverse Events of Special Interest**

AEs of Special Interest are defined in the [Appendix 13](#). If a Preferred Term of AE is included in the list of PTs of the specific AESI, that AE will be considered as AESI. See the details in the [Appendix 13](#).

CONFIDENTIAL

207660

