#### 10.13.3. Possible Distant Spread of Toxin

This AESI will be identified using the Preferred Term as below.

Accommodation disorder
Aspiration
Bradycardia
Botulism
Bulbar palsy
Constipation
Cranial nerve palsies multiple
Cranial nerve paralysis
Diaphragmatic paralysis
Diplopia
Dry mouth
Dysarthria

CONFIDENTIAL

207660

Dysphagia
Dysphonia
Dyspnoea
Extraocular muscle paresis
Eyelid function disorder
Eyelid ptosis
Facial paresis
Facial paralysis
Hyporeflexia
Hypotonia
Illeus paralytic
Muscular weakness
Paralysis
Paresis cranial nerve
Pelvic floor muscle weakness
Peripheral nerve palsy
Peripheral paralysis
Pneumonia aspiration
Pupillary reflex impaired
Respiratory arrest
Respiratory depression
Respiratory failure
Speech disorder
Urinary retention

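### The 'Possible Distant Spread of Toxin' AESI is flagged by Preferred Term alone, so local elbow weakness, expected mainly in the 400-unit arm, cannot be told from remote spread in the blind-phase AESI tables

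*SAP*

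**What the plan says.** The operative text is the amended RAP. Its section 10.13.3 introduces a list of terms with "This AESI will be identified using the Preferred Term as below", the same sentence as in 9.13.3 of the April 2018 RAP. Section 10.4.2.1 makes the match sufficient: "If a Preferred Term of AE is included in the list of PTs of the specific AESI, that AE will be considered as AESI". Neither section mentions body site, side, distance from the injected muscles or medical review, and section 8.2 adds nothing of that kind.

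The amended list keeps "Muscular weakness", Hypotonia, Hyporeflexia, Paralysis, Peripheral paralysis and Peripheral nerve palsy. The amendment did revisit the list. Its log says "Removed the two following PT to identify AESI since these were included in the list by mistake", naming Paralysis flaccid and VIIth nerve paralysis. No site criterion was added.

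On dosing, section 2.3 gives both blind-phase arms the same hand and wrist treatment: "240 units of the product will be injected into the muscles that act on the finger (including thumb flexors) and wrist flexors". The 400-unit group also receives "160 units into the muscles that act on the elbow flexors". For the 240-unit group, "Placebo will be injected into the muscles that act on the elbow flexors". After that, "In the Open-label phase, a total of 400 units will be injected in both groups".

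The blind-phase AESI tables set 240U beside 400U: 3.25 and 3.26 at the interim, 3.95 and 3.96 at the final analysis.

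**The concern.** The trial's primary endpoint is a reduction in the elbow-flexor MAS score, so lower tone in those muscles is the intended effect. Excess weakness or low tone there, if reported as an adverse event, is an extension of that local effect and not evidence that toxin has travelled. Under the Preferred Term rule the two are counted together.

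The arms do not share this equally. By design, toxin in the elbow flexors is the one blind-phase difference between them. A local elbow event caused by toxin injected there can arise only in the 400-unit arm, and it would appear in the row that readers will use to judge remote toxicity of the higher dose. Comparing the safety of 400 units with 240 units is a stated secondary objective, and the interim tables are produced for regulatory submission.

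**Working it through.** **No figure to reproduce.** The SAP states no expected rate for this AESI or for local weakness, and it tests no hypothesis. The check is textual, with an illustration of scale.

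**Step 1: what the rule captures.** Sections 10.4.2.1 and 10.13.3 together require only that an event's Preferred Term is on the list. Six listed terms (named above) carry no location. An event of elbow-flexor weakness coded to Muscular weakness meets the rule.

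**Step 2: where the arms differ (section 2.3).**

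| Site, Blind Phase | 400-unit arm | 240-unit arm | Difference |
|---|---|---|---|
| Finger, thumb and wrist flexors | 240 units | 240 units | 0 |
| Elbow flexors | 160 units | placebo | 160 units |

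Local hand and wrist events can enter both arms. Only the elbow part is differential. In the open-label cycles both groups receive 400 units, so there is no designed asymmetry between them. The overall-period tables (3.24, 3.94) do include the blind-phase events.

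**Step 3: scale.** With 60 randomised per arm, one participant is 1/60 = 1.7 percentage points, and four would be 4/60 = 6.7 points. (The Safety 1 denominator may be slightly smaller.)

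Let *b* be the AESI rate common to both arms (true spread plus local hand and wrist events), and *l* the rate of local elbow events, in the 400-unit arm only. Taking the two as independent:

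- rate in the 400-unit arm = 1 − (1 − *b*)(1 − *l*); rate in the 240-unit arm = *b*
- difference due to local elbow events = *l*(1 − *b*)
- chance of at least one such participant = 1 − (1 − *l*)^60

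Both rates are assumptions: *b* from 0% to 5%, *l* from 1% to 10%.

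| Assumed *l* | Difference, *b* = 5% to 0% | Expected participants of 60, *b* = 0 | Chance of at least one |
|---|---|---|---|
| 1% | 0.95 to 1.0 points | 0.6 | 45% |
| 2% | 1.9 to 2.0 points | 1.2 | 70% |
| 5% | 4.75 to 5.0 points | 3.0 | 95% |
| 10% | 9.5 to 10.0 points | 6.0 | 99.8% |

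**Step 4: does anything else in the SAP separate the two?** Blind-phase adverse events are tabulated by Preferred Term and arm (Tables 3.02, 3.03, 3.62, 3.63). Listings 22 and 53 carry the AESI flag, and Listings 24 and 55 relate Preferred Term to verbatim text. A reader could trace cases by hand. No planned table sorts them by site.

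**The case against.** The category is named Possible Distant Spread of Toxin. Over-capture in a safety screen is a conservative choice, and the list contains other non-specific terms such as Constipation and Dry mouth. This stands, and is why the screen and its total should be kept. A reader might infer that the plan declares every weak elbow to be distant spread. It does not: a flagged event is a possible case only.

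It can also be said that the source is not hidden, because an excess of Muscular weakness would show in the Preferred Term tables beside, say, Dysphagia or Diplopia. That is partly right. A reader might infer that a real remote signal could not be seen anywhere in the output, which goes too far. But a term such as Muscular weakness gives no site even there, so the gap in the AESI comparison remains.

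The magnitude is assumed. Even four participants against none, 4/60 versus 0/60, gives a two-sided Fisher p of about 0.12. Whether reduced tone in a target muscle is reported as an adverse event at all, and how it is coded, depends on the protocol and on coding practice, which are not at hand; the same holds for any medical review of AESIs. The documents therefore support a mechanism with a known direction, not an estimated bias.

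A remedy that sorted events into injected upper limb versus elsewhere would be wrong. In the Blind Phase, forearm pronators and shoulder muscles are not among the muscles listed for injection (sections 6.8 and 8.6), so weakness there lies beyond the injected muscles although it is in the same limb. Nor can events after the Week 24 cut-off be classified before the interim unblinding. The fix below allows for both.

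Finally, both lists spell one term 'Illeus paralytic'. A reader might infer that paralytic ileus will be missed. Section 10.4.2.1 speaks of a term being in the list and does not prescribe a literal string match, so this is a clerical error and no more.

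**Conclusion.** The point holds in limited form. The AESI flag has no site condition, its list includes non-localised terms, and the blind-phase arms differ exactly in whether the elbow flexors contain toxin. Local elbow weakness or low tone that is reported and coded to a listed term would therefore be counted mainly in the 400-unit arm, and Tables 3.25, 3.26, 3.95 and 3.96 could not tell it from remote spread. The differential part concerns the elbow only and arises in the Blind Phase only.

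The size cannot be derived from the SAP. Each participant is worth 1.7 points. An assumed local elbow rate of 2% to 5% would produce a difference of about 2 to 5 points with no difference in true spread. Because the analysis is descriptive, what is affected is the reading of a prespecified safety comparison, not any error rate or the primary efficacy result. It is worth correcting, because the change is small and loses no information.

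**What to change.** Amend sections 8.2, 10.4.2.1 and 10.13.3 as follows.

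1. Keep the Preferred Term screen and its total as the main row.
2. For the six non-localised terms, add three sub-rows to Tables 3.24 to 3.27 and 3.94 to 3.99: at a muscle group injected in that cycle; elsewhere, including uninjected muscles of the same limb; site unclear.
3. Assign the sub-row from the verbatim term and the injection record. Count a muscle group as injected whether it received active product or placebo, so that one rule applies in both arms and classification does not reveal the arm.
4. Classify events up to the Week 24 cut-off before the interim unblinding. Classify later events, including blind-phase events in participants not yet retreated at Week 24, by the same written rule, without reference to arm, before the final freeze.
5. State that the arm comparison is read from the total together with the elsewhere and unclear rows. Elbow events in the 240-unit arm fall in the injected row although only placebo was given there, so the total must not be set aside.
6. Correct the spelling of 'Illeus paralytic' as an editorial matter.

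The cost is SAP wording, extra table rows and a short review of what are likely to be few events, from verbatim text and exposure data already planned for listing. The drawback is that some events will have no determinable site. They stay visible in their own row and in the total.

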## CONFIDENTIAL

207660

## 1. INTRODUCTION

### 1.1. RAP Amendments

Revision chronology:

RAP Section	Amendment Details
Reporting and Analysis Plan_Study207660_Final_V1 02-Apr-2018	
Reporting and Analysis Plan_Study207660_Amendment_Final_V1 20-Aug-2018	
Section 2.1.	
 
Added Changes to the Protocol Defined Statistical Analysis Plan
 

Section 3.1. Interim analyses	
 
Added the definition of the Rehabilitation data used for the interim analysis
 
Changed that Cardiovascular event will not be output in the interim analysis.
 

Section 5.4.1.	
 
Clarified that a randomization stratum is Baseline MAS value "of the elbow" in this study.
 

Section 6.4. "Summary of Baseline Efficacy Parameter"	
 
Removed the MAS in the pronation of forearm and shoulder flexors from the summary table since the associated baseline value was not planned to be collected.
 
Clarified a joint location of NRS used for the summary table.
 
Added Baseline MAS score of the elbow as randomization strata in the item list of this summary table.
 
Clarified whether these items are continuous or categorical.
 

Section 6.7.Section 6.8.	
 
Added the plans for listing of Other Surgical Procedure and displays about actual dose by muscle region and joint.
 

Section 6.6. Category of Frequency	
 
Corrected the category from ">8 days per month" to ">0 and ≤8 days per month"
 

Section 7.1.1.	
 
Clarified which visit the endpoint is.
 

Section 7.2.5.1. Secondary Efficacy Analyses	
 
Clarified that the Main Assessment Parameter of DAS is used for the secondary efficacy analysis.
 
Clarified whether the fixed effects are categorial or continuous.
 
Clarified the secondary efficacy analysis for the Responder Rate of MAS score.
 
Changed the definition of Responder of MAS in the thumb to that of which denominator does not include the unevaluable thumb.
 

Section 7.3.1. Modified Ashworth Scale	
 
Removed change from baseline in MAS scores of the pronation of the forearm and should flexors since the corresponding baseline values were not collected.
 

Section 7.3.2. Numeric Rating Scale for Pain	
 
Removed change from baseline in NRS except for that of the elbow since the corresponding baseline values were not collected.
 

Section 7.3.3. Disability Assessment Scale Section 7.3.4. Clinical Global Impression of	
 
Clarified the data used for the summary tables and figures.
 

## CONFIDENTIAL

207660

RAP Section	Amendment Details
Change of functional disability	
Section 7.3.6. Time to Patient-Reported Onset of Spasticity Symptom Relief	
 
Added the derivation of time to event data in case that the participant does not complete Visit 2 and is withdrawn from study later than the planned date of Visit2.
 

Section 7.3.7. Time to Qualification for retreatment	
 
Removed ITT4 population from the time to qualification for retreatment analysis since participants who were treated 4 times were not assessed to be retreated.
 

Section 8.1.	
 
Added the plan for summary of AE within 84 days by sex and age group.
 

Section 8.3.	
 
Added the details of Worst case urinalysis.
 

Section 8.5.	
 
Added Patient Profiles analysis
 

Section 10.3 Assessment Windows	
 
Added the definition of assessment windows for efficacy analyses. The rationale was also added in the section.
 

Section 10.4.1.	
 
Changed the definition of study phases for concomitant medication.
 

Section 10.4.2.	
 
Corrected the definition of Study Phase for AE to that for which AE start time is not used since the previous definition was not that of AE which occurred within 84days.
 

Section 10.5.2.	
 
Added the plan for 95% confidence interval in summary tables for continuous efficacy endpoints.
 

Section 10.6.2 Age Category	
 
Changed the definition of Age Category to that of EudraCT requirement.
 

Section 10.12.4.	
 
Corrected the analysis population of "Summary of Race and Racial Combinations" from Enrolled to ITT1 because of baseline characteristics evaluation.
 

Section 10.12.5.2.	
 
Added the summary tables of efficacy endpoints in Open Label Phase (2nd treatment)
 

Section 10.14.	
 
Added the decision tree to determine data cutoff visit and date.
 

Section 10.13.	
 
Removed the two following PT to identify AESI since these were included in the list by mistake. 
 
Paralysis flaccid
 
Vllth nerve paralysis
 
 
 

CONFIDENTIAL

207660

## 2. SUMMARY OF KEY PROTOCOL INFORMATION

### 2.1. Changes to the Protocol Defined Statistical Analysis Plan

There was one change to the originally planned statistical analysis specified in the protocol amendment 02 [(Dated: 06OCT2017)] as the following Table shows:

Protocol	Reporting & Analysis Plan	
Objectives and endpoints	Statistical Analysis Plan	Rationale for Changes

 
Exploratory endpoints
 
Changes in MAS score from baseline in finger, thumb, wrist, elbow, pronation of the forearm and shoulder flexors
 
	
 
Change from baseline in MAS scores of the finger, thumb, wrist and elbow only will be calculated, whereas those of the pronation of the forearm and shoulder will not.
 
	
 
MAS scores in the pronation of the forearm and shoulder flexors were not collected in Blind Phase.
 
Since baseline value is defined as the latest value prior to the initial treatment, the baseline value would be usually the data at Visit1 in Blind Phase.
 
Therefore, there were not the data of the baseline value in the pronation of the forearm and shoulder flexors, and changes from baseline cannot be calculated.
 

### 2.2. Study Objective(s) and Endpoint(s)

Objectives	Endpoints
Primary Objectives	Primary Endpoints

 
To evaluate the efficacy of the injections of 400 units of the product at Week 6 (finger/ wrist flexors: 240 units, elbow flexors: 160 units), comparing to that of 240 units (finger/ wrist flexors: 240 units, elbow flexors: placebo).
 
	
 
The responder rate: The rate of the participants that Modified Ashworth Scale (MAS) score was reduced at least 1 from baseline in the elbow flexors.
 

Secondary Objectives	Secondary Endpoints

 
To evaluate the efficacy of 400 units of the product, comparing to 240 units of the product
 
	
 
The responder rate of MAS score from baseline in the finger, thumb and wrist flexors
 
Changes in MAS score from baseline in the finger, thumb, wrist and elbow flexors
 
Changes in Disability Assessment Scale (DAS) from baseline
 

	
 
Adverse events
 
Physical examinations
 
Clinical laboratory tests (haematology, blood biochemistry, urinalysis)
 

 
To evaluate the safety and tolerability of the product of 400 units, comparing to 240 units of the product/ To evaluate the safety
 
	

Objectives	Endpoints
and tolerability of 400 units of the product	
 
Vital signs (heart rate, blood pressure, body temperature)
 

Exploratory Objectives	Exploratory Endpoints

 
To evaluate the efficacy of 400 units of the product
 
	
 
Changes in MAS score from baseline in finger, thumb, wrist, elbow, pronation of the forearm and shoulder flexors
 

 
To evaluate the other efficacy of the product of 400 units, comparing to 240 units of the product/ To evaluate the other efficacy of 400 units of the product
 
	
 
Changes in Numeric Rating Scale (NRS) for pain from baseline
 

	
 
Changes in other items of DAS from baseline
 

	
 
Clinical Global Impression of Change (CGI) of functional disability by an investigator
 

	
 
CGI of functional disability by a patient
 

	
 
Time to patient-reported onset of spasticity symptom relief
 

 
To evaluate neutralizing antibody production
 
	
 
Patient-reported benefit of injection
 

	
 
Time to qualification for retreatment
 

	
 
Testing for neutralizing antibody
 

### 2.3. Study Design

Overview of Study Design and Key Features	

The diagram illustrates the study design timeline. It begins with a 'Screening' phase. This is followed by a 'Double-blind treatment' phase lasting 12 weeks, labeled as 'Part 1'. In this phase, participants are randomized to receive either 'BOTOX 400 U' or 'BOTOX 240 U + Placebo'. After the double-blind phase, the study enters an 'Open-label treatment' phase lasting 36 weeks, which is divided into three parts: 'Part 2', 'Part 3', and 'Part 4'. All participants in the open-label phase receive 'BOTOX 400 U'. Arrows labeled 'dose' indicate the timing of each injection.
	
Design Features	
This study includes a Screening Phase, Blind Phase, and Open-label Phase. The study design of each treatment phase is shown below.
 
 
Blind Phase: Multicenter, randomized, double-blind, placebo-controlled, parallel-group comparison design
 
Open-Label Phase: Multicenter, uncontrolled, open-label design
 

Dosing	
 
In the Blind Phase, participants will be randomly assigned 1:1 to either the 400 or the 240-unit group.
 
In the 400-unit group, 240 units of the product will be injected into the
 

## CONFIDENTIAL

207660

Overview of Study Design and Key Features	
	
muscles that act on the finger (including thumb flexors) and wrist flexors, and 160 units into the muscles that act on the elbow flexors. A total of 400 units of the product will be injected.
 
 
• In the 240-unit group, 240 units of the product will be injected into the muscles that act on the finger (including thumb flexors) and wrist flexors. Placebo will be injected into the muscles that act on the elbow flexors. A total of 240 units of the product will be injected.
 
• In the Open-label phase, a total of 400 units will be injected in both groups. 
 
• The product can be injected up to 3 times after completion of Part 1 in the blind phase. Participants whom the investigator considers as eligible for the injections will be treated. The next injections cannot be performed until the eligibility of the participant has been confirmed by the investigator.
 
• The muscle to be injected and the dose will be decided by the investigator based on the patient's symptoms, and a total dose of 400 units of the product will be injected in a divided dose. For the muscles that the investigator considers as unnecessary to be treated, an injection may be skipped. The involving muscle and the dose do not have to be same each time always.
 
 
 

Treatment Assignment	
 
• Number of participants (randomized participants): 120 (60 per group)
 
• GSK RandAll NG will be used to generate the randomization schedule.
 
• The randomization will be stratified by the MAS score (3 or 4) in the elbow flexors at Day1
 

Interim Analysis	
 
• Interim analysis is planned in this study as described in 3.1.
 

## 2.4. Statistical Hypotheses / Statistical Analyses

No formal hypothesis will not be tested.

## 3. PLANNED ANALYSES

### 3.1. Interim Analyses

The interim planned primary analyses will be performed after the completion of the following sequential steps:

1. All participants (except for early termination) complete the visit at Week 24 of the initial dose as defined in the protocol. The participants who complete that visit are defined as below.

The participant is re-treated at Week 12 visit in Blind Phase and completes the Week 12 visit in Open-label Phase.

The participant is re-treated at Week 16 visit in Blind Phase and completes the Week 12 visit in Open-label Phase.

